The residual variance (i.e. mean squared error) of the slope estimates will be estimated using the linear random slope model, for both the retro- and prospective slopes, to assess the reliability of slope estimation.

Homogeneity will be primarily evaluated via a shift analysis:

- A shift table of patients with categories of eGFR slopes of 1 to < 3 (slow progression) and ≥ 3 mL/min/1.73m²/year (fast progression), in each of the retrospective and prospective phases, will be provided. The shift analysis will be considered as the primary analysis to evaluate homogeneity.

Further analyses include:

- A categorical analysis of the number and proportion of patients with eGFR slopes >1 , > 3 and >5 mL/min/1.73m²/year will be provided, for both retro- and prospective phases, via tabular and graphical presentations.

- Histograms will be plotted for retro- and prospective slopes to evaluate their distributions graphically.

- The Pearson's linear correlation coefficient between retro- and prospective slopes will be derived for overall population and by patient population.

- A descriptive summary of the proportion of "shifter" and non-"shifter".

A "shifter" is defined as a patient whose:

Retrospective relative to prospective slope category shifts from slow to fast or fast to slow, respectively and

[figure not shown]
Percent change from retrospective to prospective phase slope exceeds 20%.

- McNemar's test will also be conducted to further assess the homogeneity between retro- and prospective slopes for categories of < 3 and ≥ 3 mL/min/1.73m².

In addition to the above analyses,

- A descriptive summary of the percent change in retrospective to prospective slopes will be provided.

Furthermore, the association between retrospective and prospective slopes will be assessed as a continuous endpoint, the details of which will be provided in the TSAP.

Further details of analyses will be provided in the TSAP.

FLOW CHART

Procedures should be performed in the order they appear in this flowchart.

Trial Periods	Screening	Prospective Period												
Sampling at Home and Clinic visits	1	2	3	4	5	6	7	8	9	10	11	12	13	14
Weeks	Screening ¹ -2 to 0	Baseline 1	4	8	12	16	20	24	28	32	36	40	44	48/ EOT
Days	-14 to 0	1	28	56	84	112	140	168	196	224	252	280	308	336
Permitted visit window (days)	-	0	± 4	± 4	± 4	± 4	± 4	± 4	± 4	± 4	± 4	± 4	± 4	± 4
Informed ² consent	X													

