Demographics medical history including historical creatinine data, baseline conditions.	X	X												
Check of in-/exclusion criteria	X													
Background ³ therapies (e.g. ACEis, ARBs and SGLT2)	X	X			X			X			X			X
Height	X													
Weight	X													
Physical examination	X	X			X			X			X			X
Vital signs	X	X			X			X			X			X
Optional biobanking sampling (serum, plasma, urine)		X												
First Morning Void Urine ⁴		X												X

Proprietary confidential information © 2022 Boehringer Ingelheim International GmbH or one or more of its affiliated companies

Trial Periods	Screening	Prospective Period												
		1	2	3	4	5	6	7	8	9	10	11	12	13
Sampling at Home and Clinic visits	1	2	3	4	5	6	7	8	9	10	11	12	13	14
Weeks	Screening ¹ -2 to 0	Baseline 1	4	8	12	16	20	24	28	32	36	40	44	48/ EOT
Days	-14 to 0	1	28	56	84	112	140	168	196	224	252	280	308	336
Permitted visit window (days)	-	0	± 4	± 4	± 4	± 4	± 4	± 4	± 4	± 4	± 4	± 4	± 4	± 4
Train patient on Urine and Mitra [®] sampling ⁵	X													
Provide Home sampling kits (for Urine and Mitra [®] Cartridges)		X			X			X			X			
Mitra [®] micro sampling at home ⁶			X	X		X	X		X	X		X	X	
Mitra [®] micro sampling at clinic visits		X			X			X			X			X
Provide training on smartphone/ tablet application including provision of app /device ⁷		X			X			X			X			
Mitra [®] micro sampling at Home paper diary handout (where electronic capture is not used)		X			X			X			X			
Review of home Mitra [®] sampling and Urine via application or paper diary (to be collected)					X			X			X			X
eGFR (central laboratory) ⁸	X	X			X			X			X			X
Safety laboratory		X			X			X			X			X

[figure not shown]
Proprietary confidential information © 2022 Boehringer Ingelheim International GmbH or one or more of its affiliated companies

Trial Periods	Screening	Prospective Period												
Sampling at Home and Clinic visits	1	2	3	4	5	6	7	8	9	10	11	12	13	14
Weeks	Screening ¹ -2 to 0	Baseline 1	4	8	12	16	20	24	28	32	36	40	44	48/ EOT
Days	-14 to 0	1	28	56	84	112	140	168	196	224	252	280	308	336
Permitted visit window (days)	-	0	± 4	± 4	± 4	± 4	± 4	± 4	± 4	± 4	± 4	± 4	± 4	± 4
All AEs/SAEs	X	X			X			X			X			X
Completion of patient participation														X

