1. Screening assessments may be conducted over more than one day. The baseline may start as soon as all screening procedures have been performed and laboratory results have been received and reviewed. Therefore the 14 days prior to enrollment that are indicated in the [flow chart](#) may be less. The timepoint of baseline (Visit 2) defines Day 1.
 - Screening procedures may be repeated if the patient is not eligible due to a transient medical condition (e.g. elevation of certain lab parameters due to an acute infection).
 - If the patient currently does not fulfil all inclusion/exclusion criteria but may in the opinion of the investigator fit the criteria later, the patient can be re-screened once if screening into this trial is still open. Re-screening examinations will only be performed after a written informed consent has been obtained again from the patient and is to be documented in relevant source document.
 - If screening is not completed within 14 days, the patient will be a screen failure. If appropriate the patient may be re-screened (see above).
 - Once screening assessments have been completed, a member of the trial team will contact the patient by phone to provide confirmation about eligibility.
2. Informed consent does not need to be obtained on the day of the screening visit but must be obtained before the first screening assessment. The consent discussion should include showing the patient the home sampling kits and explaining the procedures involved in the trial.
3. Any changes to the background therapies that could have an impact on eGFR slopes during trial must be captured in the relevant section of eCRF/source documents.
4. First Morning Void Urine for UACR estimation. Patients are advised to collect their urine 2 times for each visit planned in the protocol (total 4 urine samples). i.e. a day before baseline visit and on baseline visit (Visit 2/Day 1) and on day before EOT visit and on EOT visit.
5. Training on how to use the Mitra[®] microsampling device and how to do the FMV urine sampling will be provided to the patient at the screening visit. This will include instructions regarding sample shipments / what to bring in for clinic visits.

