3. DESCRIPTION OF DESIGN AND TRIAL POPULATION

3.1 OVERALL TRIAL DESIGN

This trial is a multicentre, non-randomized, low-intervention trial that does not involve administration of study drug and includes both a retrospective and prospective phase in patients with chronic kidney disease who are on stable background treatment according to respective local guidelines.

The trial targets to enrol at least 33% (up to 60%) of non DKD patients; the remaining patients will consist of DKD patients.

[figure not shown]
In this study, eGFR slopes will be calculated from historically available creatinine values (retrospective phase of study) that were collected during routine clinical care of the patients prior to enrolment in this study. In the prospective phase of the study, creatinine values will be systematically collected at predefined time points. The eGFR slopes will then be calculated from the retrospective and prospective phases.

A schematic illustration of the trial design is presented in Figure 3.1: 1.

Retrospective phase: At least 4 Serum Creatinine measurements at minimum. However, it is desirable to have as many as available.

Prospective phase: 48 weeks duration.

Site visits – Blood sample collection at baseline and every 12 weeks (i.e. Week 12, Week 24, Week 36, Week 48). Urine sample collection (for UACR determination) at baseline and Week 48. At home (using Mitra® Device) blood samples will be collected on a biweekly basis for the first 12 weeks and thereafter on a 4-weekly basis until Week 48. If site visit coincides, Mitra® device sample will be collected in combination with venous sample on site.

* Screening period of up to 2 weeks between retrospective and prospective phases.

Baseline visit is considered as Visit 2/Day1 of prospective phase

Figure 3.1: 1 Trial design

Patients will be screened in the trial once they have signed the informed consent. They will undergo a screening period of up to 2 weeks from the time of informed consent. All available historical eGFR values, UACR/PCR within the 5.5 years prior to screening Visit 1 will be

collected for each patient. Patients who successfully complete the screening and meet the inclusion / exclusion criteria, including the availability of requisite historical eGFR data, will qualify for enrollment into the 48 weeks prospective phase of the study (see [Figure 3.1: 1](#)).

Retrospective phase:

To be documented in the CRF:

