5.1.1 Creatinine

Serum creatinine:

Samples for the determination of serum creatinine will be collected at the time points indicated in the [flow chart](#) and analysed at a central laboratory using the enzymatic method.

Creatinine from capillary blood:

Using the Mitra[®] microsampling device (with two tips per cartridge, each capable of absorbing 10 uL of blood) two blood samples will be collected after a finger prick with the supplied lancet at the time points indicated in the flow chart. The closed cartridge will be shipped to the central laboratory. Details of shipment procedures will be provided in the laboratory manual in the ISF and the instructions to the patient. Samples will be analysed using a validated mass spectroscopy method.

All capillary blood samples remaining at the end of the study will be destroyed no later than the sign-off of the clinical trial report.

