#### 4.11.2 Clinical Laboratory Evaluation

The analyses of laboratory data will be descriptive in nature. Analyses will be based on SI units and on standardized values for all parameters except urine albumin, urine protein, urine creatinine, UACR and PCR, which will be reported in the conventional units. Results from the central laboratory will be included in the reporting of this study for the following laboratory groups:

- Hematology
- Chemistry
- Urine Chemistry.

Laboratory parameters will be collected at the following visits, as per the CTP (for all parameters except eGFR collected at home via Mitra® micro sampling):

- Baseline (visit 2)
- Visit 5
- Visit 8
- Visit 11
- Visit 14 (end of study visit).

For eGFR collected at home via Mitra® micro sampling, these will additionally be collected at visits 3, 4, 6, 7, 9, 10, 12, 13 and will be collected bi-weekly at visits 2, 3 and 4.

For by-visit summaries, the last non-missing assessment (including repeat assessments) recorded at each visit will be summarized. In the case that there are multiple measurements taken on the same date and time, and these measurements are simultaneously the last non-missing assessment at a visit, then the mean of these measurements will be taken and this average will be used in the analysis. Unscheduled visits will not be included in the summary tables. Listings will present all visits, including unscheduled ones.

At each visit, laboratory measurements will be compared with the relevant laboratory reference ranges and categorized as abnormal (low/high) or normal:

- Low: below the lower limit of the laboratory reference range
- Normal: within the laboratory reference range (upper and lower limit included)

- High: above the upper limit of the laboratory reference range.

Descriptive summaries of the baseline, post-baseline and change from baseline in laboratory parameters will be presented by laboratory parameter and visit. Additionally, a summary of the number and percentage of patients with abnormal laboratory values will be presented by laboratory parameter and visit. Percentages will be based on the number of patients with a measurement at the visit (per parameter).

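### Under SAP 4.11.2, the by-visit Mitra eGFR summaries would show Week 6 and Week 10 home samples as Visit 3 (Week 4) and Visit 4 (Week 8)

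*SAP*

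**What the plan says.** **Sampling frequency.** Protocol 3.1 states that "blood samples will be collected on a biweekly basis for the first 12 weeks and thereafter on a 4-weekly basis until Week 48". Protocol 1.4.2, flow-chart footnote 6 and SAP Figure 3.1:1 give the same schedule.

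**Flow-chart grid.** The prospective columns are Day 1 (Visit 2) and then every fourth week from Week 4 (Visit 3) to Week 48 (Visit 14). The row marked "micro sampling at home ⁶" has entries at Visits 3, 4, 6, 7, 9, 10, 12 and 13 only. Visit 2 is marked for clinic Mitra sampling, not home sampling. The windows are 0 days at Visit 2 and ± 4 days at each later visit. Footnote 1 adds that "The timepoint of baseline (Visit 2) defines Day 1".

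**SAP visit assignment.** SAP 4.11.2 repeats the grid's home visits and adds that these samples "will be collected bi-weekly at visits 2, 3 and 4".

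**SAP selection rule.** For by-visit tables, the same section says that "the last non-missing assessment (including repeat assessments) recorded at each visit will be summarized". Its only provision for several candidate values is to average those that share the same date and time.

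**SAP baseline rule.** SAP 4.2 takes, for each domain, the most recent value up to and including Visit 2. It does not say whether Visit 2 there means a calendar date or a visit label.

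**The concern.** The sampling text creates three time points, Weeks 2, 6 and 10, that the grid does not number. The SAP attaches them to Visits 2, 3 and 4, so each of those visits holds two samples about two weeks apart. A rule that keeps the last value then discards the sample belonging to the nominal time and keeps the later one.

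A table row that readers take as Week 4 or Week 8 would therefore hold Week 6 or Week 10 values. The row would also be mixed, because a patient who misses the Week 6 sample falls back to Week 4 and nothing in the table shows this. If the same logic reached Visit 2, a home sample taken after Day 1 could stand in for the Day 1 clinic sample in the Visit 2 summary. At stake are the labelling and interpretation of descriptive tables.

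**Working it through.** The plan states no figure on this point, so there is none to reproduce. The check applies the documents' own rules to a patient with every sample.

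**1. Count the time points.** Every two weeks to Week 12: Weeks 0, 2, 4, 6, 8, 10, 12 (7 time points). Every four weeks from Week 16 to Week 48: 9 time points. Total 7 + 9 = 16. The grid has 13 prospective columns (Visits 2 to 14): 8 home and 5 clinic Mitra entries. The difference is 16 − 13 = 3, namely Weeks 2, 6 and 10.

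**2. Assign the three samples.** The SAP names Visits 2, 3 and 4. Visit 2 carries only a clinic Mitra sample in the grid, so a further home sample attached to it can only be Week 2. By the same logic Visit 3 holds Weeks 4 and 6, and Visit 4 holds Weeks 8 and 10.

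**3. Apply the last-non-missing rule.** Days follow the flow chart's convention (week × 7, with Day 1 for baseline).

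| Visit | Nominal day and window | Samples attached | Last sample | Days past window |
|---|---|---|---|---|
| 2 | Day 1, no tolerance | Day 1, Week 2 | Week 2, Day 14 | 14 − 1 = 13 |
| 3 | Day 28, Days 24 to 32 | Weeks 4, 6 | Week 6, Day 42 | 42 − 32 = 10 |
| 4 | Day 56, Days 52 to 60 | Weeks 8, 10 | Week 10, Day 70 | 70 − 60 = 10 |
| 5 to 14 | as in the flow chart | one time point each | nominal | 0 |

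The averaging provision does not help, because it needs an identical date and time. No window rule visible in the SAP separates the two samples at a visit.

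**4. Baseline.** The Visit 2 row above reads Visit 2 as a label. If SAP 4.2 is read by date, a sample from Day 14 is after Visit 2 and cannot be the baseline value, so change from baseline stays anchored to Day 1.

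**5. Size of the shift.** Expected change in eGFR over 14 days = annual decline × 14 / 365.25:

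- decline of 1 per year: 0.04 mL/min/1.73m²
- decline of 3 per year: 3 × 14 / 365.25 = 0.115, about 0.12
- decline of 5 per year: 0.19

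SAP 5.1 gives eGFR to 0 decimal places and SAP 4.2 prints means to one more place than the raw data. At the threshold of 3 per year, the expected shift is therefore about one unit in the last printed digit of a mean. An individual patient's two values can differ by more than this through measurement variation.

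**6. Primary analysis.** SAP 4.10.2 models eGFR on time in years from baseline and considers all prospective measurements from baseline on, subject to its stated exclusions. The visit label does not enter, so the slopes and the shift table do not depend on this assignment.

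**The case against.** Several points on the other side are sound.

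- **Baseline.** The zero-day window at Visit 2, and the statement that Visit 2 defines Day 1, favour reading SAP 4.2 by date. This stands: a misplaced baseline is possible only under the label reading.
- **Labels set elsewhere.** The SAP relies on the eCRF and the laboratory transfer specifications, which are not available here. They may give these samples their own labels. SAP 4.11.2 also speaks of when samples are collected, so filing them under those visits is an inference. This stands as a caveat, but the SAP text supplies no such label and no window.
- **Timing.** The study was terminated in July 2022, before SAP version 2.0 of 17 October 2022. A flow-chart correction cannot now change what was collected. The tables are still to be made, since SAP 3.1.1.1 says that all planned analyses will be performed.

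A reader might also draw two stronger conclusions that the documents do not support.

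- **Uneven collection between sites.** Protocol 5.1.1 says that "two blood samples will be collected after a finger prick with the supplied lancet at the time points indicated in the flow chart", so one could suppose that some sites followed the grid (13 samples) and others the text (16). But footnote 6 is attached to the home-sampling row and is part of the flow chart, and nothing shows that any site ignored it. One can calculate that 16 samples give a 12% smaller slope standard error: √(2912 / 3734) = 0.883, from the sums of squared time deviations in week². That figure measures the supposed variation in collection, not the mislabelling. It also assumes per-patient least squares with independent errors, whereas SAP 4.10.2 plans a random-slope model with an autoregressive covariance structure.
- **A spoiled comparison of Mitra with venous sampling.** Protocol 3.1 wants that comparison, but nothing visible makes the tables of SAP 4.11.2 the place for it. The visible comparison in SAP 4.10.2 runs the primary analysis once per source, and further analyses are redacted.

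**Conclusion.** The point holds as a minor correction to descriptive tables. Followed literally, SAP 4.11.2 reports Week 6 values under Visit 3 and Week 10 values under Visit 4 in fully sampled patients. The Visit 2 summary is affected only if Visit 2 is treated as a label. At a decline of 3 per year the expected numerical effect is about 0.1 mL/min/1.73m².

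This rests on three assumptions: that Mitra eGFR is among the parameters in the by-visit laboratory tables, as the structure of SAP 4.11.2 implies; that the extra samples carry the visit labels the SAP names; and that no separate windowing rule exists in the eCRF or transfer specifications. A reader might infer that the primary result is at risk. It is not.

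**What to change.** In SAP 4.11.2:

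- give the Week 2, 6 and 10 home samples their own nominal time points, assigned by sample date;
- restrict the Visit 2, 3 and 4 summaries to samples inside the protocol windows (Day 1, Day 28 ± 4, Day 56 ± 4);
- state that the Mitra baseline is the Day 1 sample, which also settles how SAP 4.2 is to be read for this parameter.

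For the record, the flow-chart grid and its footnote 6 should be reconciled, so that the set of expected samples is unambiguous when missing samples are counted.

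The cost is a few lines of SAP text and a date-based visit-mapping step in programming. No new data are needed, and the primary analysis does not change.

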Patients will be advised to collect 2 UACR samples for each visit planned in the protocol (total 2 visits and 4 urine samples). i.e a day before baseline visit and on baseline visit (Visit 2/Day 1) and also on day before EOT visit and on EOT visit. The patient will be equipped with urine collection containers to sample urine from their First Morning Voids in collection container (latter only for visit at which urine collection is scheduled, i.e. baseline and Week 48).

Throughout the study duration, AEs as defined in [section 5.2.6.2](#) and changes to background medication will be collected, documented and reported. Patients who receive ARBs, ACEis and SGLT2 inhibitors will be required to maintain stable treatment during the trial duration.

At the end of the 48 weeks prospective phase period, or at the time that a patient is permanently discontinued, patients will have an EOT visit. Database lock will occur after the last patients have completed their final visit.

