5.1.2 UACR

Urine samples for the determination of urine albumin creatinine ratio (UACR) will be collected by the patient at home from first morning void (FMV) urine at the baseline visit and the end of trial visit. At each visit, the patient will collect an FMV urine sample on the day before the visit and the day of the visit itself. An appropriate number of urine cups will be provided to the patient for collection at home. Patients will be reminded e.g. by telephone contacts ahead of sampling time points on how to collect and store their urine samples. Further collection and sample storage instructions are given in the laboratory manual in the ISF and instructions to the patient.

Urinary albumin and creatinine will be analysed at a central laboratory using routine validated methods.

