### 4.2 General Presentation Considerations

For each patient, the date of baseline, i.e. Day 1 of the study, is defined as the earliest assessment taken across all domains/measurements on Visit 2 of the prospective phase. For individual domains, the latest measurement on or before Visit 2 will be used as the baseline measurement. 'End of Study' is defined as the last available post-baseline assessment. For the prospective phase, 'Study Day' will be calculated relative to the date of baseline such that Study Day = Assessment Date – Date of Baseline +1. For the retrospective phase, 'Study Day' will be calculated relative to the date of baseline such that Study Day = Assessment Date – Date of Baseline (note that the resulting study day will be negative for retrospective data).

Continuous data will be summarized in terms of the mean, standard deviation (SD), median, minimum, maximum and number of observations, unless otherwise stated. Continuous data that are expected to be skewed will be presented in terms of the maximum, upper quartile, median, lower quartile, minimum and number of observations. The minimum and maximum will be reported to the same number of decimal places as the raw data recorded in the database. The mean, SD, median, lower quartile and upper quartile will be reported to one more decimal place than the raw data recorded in the database. In general, the maximum number of decimal places reported shall be 4 for any summary statistic.

Categorical data will be summarized in terms of the number of patients providing data at the relevant time point (n), frequency counts and percentages. Any planned collapsing of categories will be detailed in the SAP text and the data displays.

Percentages will be presented to one decimal place. Percentages will not be presented for zero counts. The denominator for percentages will be further specified in this SAP. If sample sizes are small, the data displays will show the percentages, but any textual report will describe frequencies only.

P-values greater than or equal to 0.001, in general, will be presented to 3 decimal places. P-values less than 0.001 will be presented as "<0.001". Confidence intervals (CIs) will be presented to one more decimal place than the raw data.

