#### 4.7 Demographic and Other Baseline Characteristics

Descriptive summaries of demographic and baseline characteristics will be presented for the FAS. For categorical summaries, the number and percentage of patients in each category will be presented, and for continuous summaries the n/mean/SD/min/median/max will be presented. Percentages will be based on the number of patients in the FAS. The number of patients with missing values for categorical summaries may be presented if any such values are present in the data.

Summaries of the following characteristics will be presented:

- Sex (male / female)
- Ethnicity (Hispanic or Latino / Not Hispanic or Latino)
- Race (American Indian or Alaska Native / Asian / Black or African American / Native Hawaiian or Other Pacific Islander / White / Multiple) – note that patients who select multiple race groups on the eCRF will be summarized as ‘multiple’
- Age (years) as collected on the eCRF
- Age category in years (<45, ≥45 to <65, ≥65)
- Height (cm)
- Weight (kg)
- Body mass index (BMI) (kg/m^2)
- Indication (DKD / Non-DKD)
- Time since first diagnosis (years)
- Country
- Baseline eGFR (ml/min/1.73m^2)
- Baseline eGFR category (<30, ≥30 to <60, ≥30 to ≤45, ≥45 to <60, ≥60 ml/min/1.73m^2)

- Baseline UACR (mg/g)
- Baseline UACR category (<30, ≥30 to <300, ≥300 mg/g).

Body mass index will be calculated as  $[\text{weight (kg)} / [\text{height (m)}]^2]$ . Time since first diagnosis will be calculated as  $[\text{date of informed consent} - \text{date of first diagnosis} + 1] / 365.25$ .

In the case that the date of first diagnosis of CKD is partial or missing, if only the day is missing then the first day of the month will be imputed. If the month and day are missing, then the first of January will be imputed. If the year or entire date is missing then no imputations will be done, and the patient will not be included in the summary of time since first diagnosis.

Demographic and baseline characteristics will also be listed. Additional to the variables mentioned above, the patient identifier, site, gender identity, childbearing potential (females only), birth year, and additional details of race group for Asians (per eCRF) will be presented.

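### Two first-morning urine samples are collected per UACR visit, but the readable SAP rules use only one of them in the UACR summaries, which adds avoidable random error to descriptive outputs

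*SAP*

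**What the plan says.** **Collection.** Protocol 3.1 states: "Patients will be advised to collect 2 UACR samples for each visit planned in the protocol (total 2 visits and 4 urine samples". Protocol 5.1.2 gives the timing: "At each visit, the patient will collect an FMV urine sample on the day before the visit and the day of the visit itself". Footnote 4 to the protocol flow chart repeats both the count and the timing. The two UACR visits are baseline and Week 48/EOT.

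**Selection for analysis.** Three SAP rules bear on which value is used:

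- SAP 4.2 says that, for each domain, "the latest measurement on or before Visit 2 will be used as the baseline measurement".
- SAP 4.11.2 says: "For by-visit summaries, the last non-missing assessment (including repeat assessments) recorded at each visit will be summarized". UACR falls under this section, which names it among the parameters reported in conventional units.
- SAP 4.11.2 also has an averaging provision, which opens: "In the case that there are multiple measurements taken on the same date and time". It applies only when those simultaneous values are also the last non-missing ones at the visit.

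**Use.** SAP 4.7 summarises baseline UACR as a continuous value and by group, "Baseline UACR category (<30, ≥30 to <300, ≥300 mg/g". SAP 4.11.2 adds summaries by visit and change from baseline. Its listings cover all visits and are not restricted to the selected value.

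**The concern.** The second void is scheduled in three places in the protocol, so it is part of the design and not an incidental repeat. The SAP then applies its generic laboratory rule, which picks one value. Voids from consecutive days do not share a collection date, so on those dates the averaging provision cannot reach them. No readable section gives a separate rule for combining them.

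What is at stake is precision. Any day-to-day variation in UACR that is not perfectly correlated across the two days passes undiminished into the baseline value, the three-group classification and the change to Week 48, although a second measurement is already in hand. Protocol 1.3 lists different starting levels of eGFR and UACR/PCR among the questions about slope estimation to be explored. If patients are grouped by baseline UACR for that purpose, the grouping carries the same avoidable error.

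**Working it through.** **1. Count.** 2 visits × 2 voids = 4 samples per patient, which reproduces the protocol's own total. The SAP rules select 1 per visit, so 2 of 4 enter the summaries when all four are supplied. If one void of a pair is missing, the other is used and nothing is lost.

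**2. Error of one value against the mean of two.** Work on the log scale. Let the day-to-day SD be s and the correlation of the two days' errors be ρ. One void has error SD s. The mean of the two logs (a geometric mean) has error SD s × √((1 + ρ)/2). The ratio to one void is:

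- ρ = 0: √0.50 = 0.71 (a reduction of 29%)
- ρ = 0.3: √0.65 = 0.81 (19%)
- ρ = 0.6: √0.80 = 0.89 (11%)

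The ratio is below 1 for every ρ below 1, so the direction needs no further assumption.

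**3. Misclassification at 30 and 300 mg/g.** The documents give no UACR distribution and no day-to-day variability, so these inputs are assumed: true UACR log-normal, median 200 mg/g, log-SD 1.6, and s of 0.3, 0.4 or 0.6. A patient is misclassified when the measured group differs from the group of the true value. Integrating over the true distribution gives:

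| Daily log-SD s | One void | Mean of two, ρ = 0 | ρ = 0.3 | ρ = 0.6 |
|---|---|---|---|---|
| 0.3 | 8.7% | 6.2% | 7.0% | 7.8% |
| 0.4 | 11.5% | 8.2% | 9.3% | 10.3% |
| 0.6 | 17.1% | 12.2% | 13.9% | 15.4% |

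**4. A wider assumed range.** Take medians of 50 to 400 mg/g, between-patient log-SD of 1.2 to 1.8, day-to-day CV of 20% to 70%, and independent days. Misclassification runs from about 5% to 21% with one void and from about 3% to 15% with the geometric mean of two. The ratio is about 1.4 throughout. On the planned 600 patients that is 8 to 35 fewer misclassified. An arithmetic mean of the two voids does nearly as well: at median 150 mg/g, log-SD 1.2 and CV 70%, the rates are 20.5% (one void), 14.7% (geometric mean) and 15.3% (arithmetic mean).

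**5. Change from baseline.** With errors independent between visits and between days, the error SD of the log change is s√2 with one void per visit and s with two. For s = 0.3, 0.4 and 0.6 it falls from 0.42, 0.57 and 0.85 to 0.30, 0.40 and 0.60.

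**The case against.** Several points on the other side have force.

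- **Last value is a workable convention.** The SAP states it in advance and applies it consistently. The documents do not say why two voids are taken. If the second is a backup, choosing the last non-missing value is coherent. This stands as a reason to call the change an improvement in efficiency and not the repair of a contradiction. It does not remove the loss of precision when both voids are present.
- **Half of the UACR data are thrown away.** A reader might infer this, but the documents do not support it. The unselected void is not excluded from the listings, it serves when the other is missing, and the retrospective UACR/PCR values collected under Protocol 3.1 are not touched.
- **The analysis of slopes by UACR is compromised.** A reader might infer this too. Parts of the SAP are blacked out, including contents entries between 4.10.2 and 4.11, and a UACR-specific derivation could sit there. The claim is therefore limited to SAP 4.2, 4.7 and 4.11.2, which contain no exception. A different rule elsewhere would leave two definitions of baseline UACR to align.
- **Dating of samples.** How the two voids are dated and labelled in the data depends on the laboratory transfer specifications, which are not available. By collection date the averaging provision does not apply, but the data files cannot be checked.
- **The sizes are assumed.** This is right. Defining the true value on the log scale also favours the geometric mean somewhat.
- **Little depends on it.** The visible uses are a baseline table and descriptive laboratory summaries. The study was terminated in July 2022, so counts per 600 describe the planned cohort only, and the number of patients with paired UACR visits is not stated.

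**Conclusion.** The point holds as a minor one. Under the readable SAP rules, when both voids are available only one enters the baseline UACR value and category, the visit summaries and the change from baseline.

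The consequence is avoidable random error in those outputs and in any grouping by baseline UACR. It would be wrong to read it as bias, since nothing in the documents suggests that the visit-day void differs systematically from the day-before void. It would also be wrong to read it as a threat to the main result: the primary model in SAP 4.10.2 is unadjusted and the shift table does not use UACR.

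That the error shrinks when both voids are used is certain for anything short of perfectly correlated days. How far it shrinks is not known from the documents. The falls in section 3 of the working rest on an assumed UACR distribution and on daily SDs that the documents do not supply, and roughly two thirds of the gain in classification disappears if the two days' errors correlate at 0.6.

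**What to change.** Add one sentence to SAP 4.2 and 4.11.2, and apply it in 4.7: UACR at baseline and at Week 48/EOT is the geometric mean of the available first-morning voids from the day before and the day of the visit; if only one is available, that value is used. Use the result for the baseline value and category, the visit summaries and the change from baseline, and align any other UACR derivation in the SAP with it.

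The cost is SAP wording and a few lines of code. No new samples and no change to conduct are needed. The one drawback is that patients with a single void have a slightly noisier value than those with two, so the number contributing one and two voids should be reported.
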